3.3.2.5 Management of diarrhea

Appearance of grade 1-2 diarrhea attributed to study drug toxicity may be treated with supportive care such as loperamide, initiated at the earliest onset (for example 4 mg orally followed by 2 mg orally every 2 hours until resolution of diarrhea).

3.3.2.6 Management of hyperlipidemia and hyperglycemia

Adverse Drug Reaction	Severity	Everolimus Dose Adjustment and Management Recommendations
Metabolic events (e.g. hyperglycemia, dyslipidemia)	Grade 1	No dose adjustment required. Initiate appropriate medical therapy and monitor.
	Grade 2	No dose adjustment required. Manage with appropriate medical therapy and monitor.
	Grade 3	Temporary dose interruption. Re-initiate everolimus at lower dose. Manage with appropriate medical therapy and monitor.
	Grade 4	Discontinue everolimus and treat with appropriate medical therapy.

3.3.2.7 Management of non-infectious pneumonitis

Non-infectious pneumonitis is a class effect of rapamycin derivatives. Cases of non-infectious pneumonitis (including interstitial lung disease) have also been described in patients taking everolimus. Some of these have been severe and on rare occasions, a fatal outcome was observed.

- A diagnosis of non-infectious pneumonitis should be considered in patients presenting with non-specific respiratory signs and symptoms such as hypoxia, pleural effusion, cough or dyspnea, and in whom infectious, neoplastic and other non-medicinal causes have been excluded by means of appropriate investigations. Patients should be advised to report promptly any new or worsening respiratory symptoms.

If non-infectious pneumonitis develops, the guidelines in Table 3-4 should be followed. Consultation with a pulmonologist is recommended for any case of pneumonitis that develops during the study.

Table 3-4: Management of non-infectious pneumonitis

Worst grade pneumonitis	Suggested investigations	Management of pneumonitis	Everolimus dose adjustment
Grade 1 (Asymptomatic, radiographic findings only)	CT scans with lung windows.	No specific therapy is required	No dose adjustment required. Initiate appropriate monitoring.
Grade 2 (Symptomatic, not interfering with Activities of Daily Living)	CT scan with lung windows. Consider pulmonary function testing includes: spirometry, DLCO, and room air O ₂ saturation at rest. Consider a bronchoscopy with biopsy and/or BAL. Monitoring at each visit until return to ≤ grade 1. Return to initial monitoring frequency if no recurrence.	Symptomatic only. Consider corticosteroids and/or other supportive therapy if symptoms are troublesome.	Rule out infection and consider interruption of everolimus until symptoms improve to Grade ≤ 1. Re-initiate everolimus at one dose level lower. Discontinue everolimus if failure to recover within ≤ 28 days.
Grade 3 (Symptomatic, Interfering with Activities of Daily Living. O ₂ indicated)	CT scan with lung windows and pulmonary function testing includes: spirometry, DLCO, and room air O ₂ saturation at rest. Monitoring at each visit until return to ≤ grade 1. Return to initial monitoring frequency if no recurrence. Bronchoscopy with biopsy and/or BAL is recommended.	Consider corticosteroids if infective origin is ruled out. Taper as medically indicated.	Rule out infection and interrupt everolimus until symptoms improve to Grade ≤ 1. Consider re-initiating everolimus at one dose level lower (approximately 50% lower than the dose previously administered depending on individual clinical circumstances) Discontinue everolimus if failure to recover within ≤ 28 days. If toxicity recurs at Grade 3, consider discontinuation
Grade 4 (Life-threatening, ventilatory support indicated)	CT scan with lung windows and required pulmonary function testing, if possible, includes: spirometry, DLCO, and room air O ₂ saturation at rest. Monitoring at each visit until return to ≤ grade 1. Return to initial monitoring frequency if no recurrence. Bronchoscopy with biopsy and/or BAL is recommended if possible.	Consider corticosteroids if infective origin is ruled out. Taper as medically indicated.	Rule out infection and discontinue everolimus.

3.3.2.8 Management of hepatitis reactivation / flare

Reactivation of Hepatitis B (HBV) has been observed in patients with cancer receiving chemotherapy.²⁹ Sporadic cases of Hepatitis B reactivation have also been seen in this setting with everolimus. Use of antivirals during anti-cancer therapy has been shown to reduce the risk of Hepatitis B virus reactivation and associated morbidity and mortality.³⁰ A detailed assessment of Hepatitis B/C medical history and risk factors must be done for all patients at screening, with testing performed prior to the first dose of everolimus.

Monitoring and prophylactic treatment for hepatitis B reactivation

Table 3-5 provides details of monitoring and prophylactic therapy according to the screening results of viral load and serologic markers testing.

Table 3-5: Action to be taken based on screening hepatitis B results

Test	Result	Result	Result	Result	Result
HBV-DNA	+	+ or -	-	-	-
HBsAg	+ or -	+	-	-	-
HBsAb	+ or -	+ or -	+ and no prior HBV vaccination	+ or -	- or + with prior HBV vaccination
HBcAb	+ or -	+ or -	+ or -	+	-
Recommendation	Pt will not be eligible for study		No prophylaxis Monitor HBV-DNA approximately every 3-4 weeks		No specific action

Antiviral prophylaxis therapy should continue for at least 4 weeks after last dose of everolimus. For HBV reactivation definition and management guidelines, see Table 3-6.

Table 3-6: Guidelines for the management of hepatitis B reactivation

HBV reactivation (with or without clinical signs and symptoms)*	
For patients with baseline results: Negative HBV-DNA and HBsAg AND [Positive HBsAb (with no prior history of vaccination against HBV), OR positive HBcAb]	Treat : Start first antiviral medication AND Interrupt everolimus administration until resolution: 
 • \leq undetectable (negative) HBV-DNA levels If resolution occurs within ≤ 28 days , everolimus can be re-started at one dose lower, if available (see Table 3-1 for dose levels available). If the patient is already receiving the lowest dose of everolimus according to the protocol, the patient should restart at the same dose after resolution. Antiviral therapy should continue at least 4 weeks after last dose of everolimus. If resolution occurs > 28 days Patients should discontinue everolimus but continue antiviral therapy at least 4 weeks after last dose of everolimus.

* All reactivations of HBV are to be recorded as grade 3 (e.g. CTCAE Version 3.0 - Investigations/Other: Viral Reactivation), unless considered life threatening by the investigator, in which case they should be recorded as grade 4. Date of viral reactivation is the date on which the rise or reappearance of HBV-DNA was recorded.

Abbreviated Title: Phase II everolimus for BHD

Version Date: March 7, 2017

Monitoring for hepatitis C flare

The following two categories of patients should be monitored every 4–8 weeks for HCV flare:

- Patients known to have a history of HCV infection, despite a negative viral load test at screening (including those that were treated and are considered ‘cured’)

For definitions of HCV flare and actions to be taken in the event of a flare, please refer to Table 3-7.

Table 3-7: Guidelines for the management of hepatitis C flare

Baseline results	HCV flare definition*	HCV flare management
Knowledge of past hepatitis C infection with no detectable HCV-RNA	New appearance of detectable HCV-RNA AND ALT elevation > 5 x ULN or 3 x baseline level, whichever is higher.	Discontinue everolimus

* All flares of HCV are to be recorded as grade 3 (e.g. CTCAE Version 4.0 - Investigations - Other: Viral Flare), unless considered life threatening by the investigator; in which case they should be recorded as grade 4. Date of viral flare is the date on which both the clinical criteria described above were met. (e.g., for a patient whose HCV-RNA increased by 2 logs on 01 JAN 2011 and whose ALT reached > 5 x ULN on 22 JAN 2011, the date of viral flare is 22 JAN 2011).

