3.3 DOSE MODIFICATIONS

3.3.1 Dose modification and dose delay

3.3.1.1 Dosing modifications

For patients who do not tolerate the protocol-specified dosing schedule, dose adjustments are permitted in order to allow the patient to continue the study treatment.

Abbreviated Title: Phase II everolimus for BHD

Version Date: March 7, 2017

All dose modifications should be based on the worst preceding toxicity. Dose modifications will be made only for those AEs thought to be related to everolimus.

For each patient, once a dose reduction has occurred, the dose level may not be re-escalated during subsequent treatment cycles with everolimus. Dose modifications will follow the scheme outlined in Table 3-1. No more than 2 dose reductions will be allowed per patient.

Table 3-1: Study treatment schedule adjustments and dose levels

Dose level	Dose and schedule*
1	10 mg PO QD
0 (starting dose)	5mg PO QD
-1	2.5mg PO QD

* Once patients have had a dose escalation to the 10mg p.o. QD dose, dose reductions for AEs will be to move to the next lower dose level.

If a patient has already decreased 2 dose levels, no further dose reduction is permitted. Patients who need an additional dose reduction will be required to discontinue everolimus.

Table 3-2 and Table 3-3 list the dosing guidelines for everolimus-related non-hematologic and hematologic toxicities.

Abbreviated Title: Phase II everolimus for BHD

Version Date: March 7, 2017

Table 3-2: Dosing guidelines for everolimus-related non-hematologic toxicities

Toxicity	Action
Non-Infectious Pneumonitis	Please refer to Table 3-4.
AST or ALT elevation	Maintain current dose level
Grade 1 (> ULN - 3.0 x ULN)	
Grade 2 (> 3.0 - 5.0 x ULN)	
AST or ALT elevation	Interrupt everolimus administration until resolution to \leq grade 1 (or \leq grade 2 if baseline values were within the range of grade 2). If resolution occurs \leq 7 days, everolimus should be re-started at the dose level prior to interruption.
Grade 3 (> 5.0 - 20.0 ULN)*	If resolution takes $>$ 7 days, or if event recurs within 28 days, hold everolimus until recovery to \leq grade 1 or baseline grade / value and reintroduce everolimus at one dose level lower, if available.
AST or ALT elevation	Discontinue everolimus.
Grade 4 (> 20 x ULN)*	

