Intolerable grade 2 mucositis, or grade 3 AE, except hyperglycemia or hypertriglyceridemia or hypercholesterolemia (see Section 3.3.2.6)	Interrupt everolimus administration until resolution to \leq grade 1 or baseline grade / value. If resolution occurs within \leq 7 days, everolimus should be re-started at the dose level prior to interruption. If resolution takes $>$ 7 days, or if event recurs within 28 days, hold everolimus until recovery to \leq grade 1 or baseline grade / value and reintroduce everolimus at one dose level lower, if available. Patients will be withdrawn from the study if they fail to recover to \leq grade 1 or baseline grade / value within 28 days.
Any other grade 4	Discontinue everolimus.
Grade 3 or 4 clinical liver failure (asterixis or encephalopathy/coma)	Discontinue everolimus
Recurrence of intolerable grade 2 mucositis or grade 3 event after dose reduction	Reduce dose to the next lower dose level, if available. The lowest possible dose level of everolimus is 2.5 mg daily. Below this level, everolimus must be discontinued. If toxicity recurs at Grade 3, consider discontinuation
Any non-hematologic toxicity requiring Everolimus interruption for $>$ 28 days	Discontinue everolimus

Table 3-3 Dosing guidelines for everolimus-related hematologic toxicities

Toxicity	Action
≤ Grade 2 thrombocytopenia (platelets <75, ≥ 50 x10 ⁹ /L)	No action
Grade 3 thrombocytopenia (platelets <50, ≥ 25 x10 ⁹ /L)	Interrupt everolimus until resolution to grade ≤1 If resolution occurs ≤ 7 days, reintroduce everolimus at the dose level prior to interruption. If resolution occurs > 7 days, or event occurs within 28 days, reintroduce everolimus at one dose level lower, if available.
Grade 4 thrombocytopenia (platelets < 25 x10 ⁹ /L)	Discontinue everolimus
Grade 3 neutropenia or anemia (neutrophil <1, ≥ 0.5 x10 ⁹ /L)	Interrupt everolimus until resolution to grade ≤1 or baseline value If AE resolution occurs ≤ 7 days, reintroduce everolimus at the same dose level. If AE resolution occurs > 7 days, or event occurs within 28 days, reintroduce everolimus at one dose level lower, if available.
Grade 4 neutropenia or anemia	Discontinue everolimus
Febrile neutropenia	Interrupt everolimus until resolution to grade ≤ 1 (or baseline value) and no fever. Reintroduce everolimus at one dose level lower, if available.*

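### Table 3-6 permits an everolimus restart after a grade 4 hepatitis B reactivation, overlapping the grade 4 stop rule in Table 3-2; Table 3-3 has a lesser overlap for febrile neutropenia

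*Combined protocol and SAP*

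**What the plan says.** **Hepatitis B, Section 3.3.2.8.** The heading of Table 3-6 reads "HBV reactivation (with or without clinical signs and symptoms". The table applies to patients who entered without HBV-DNA or HBsAg but with HBcAb, or with HBsAb and no vaccination history. It has a single management entry. An antiviral is started and everolimus is interrupted until "undetectable (negative) HBV-DNA levels". If that happens within 28 days, "everolimus can be re-started at one dose lower, if available". For a patient already on the lowest dose, "the patient should restart at the same dose after resolution". After more than 28 days everolimus stops. Antiviral treatment runs to at least 4 weeks past the final everolimus dose. The footnote grades every reactivation 3 "unless considered life threatening by the investigator, in which case they should be recorded as grade 4".

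**General dosing rules, Section 3.3.1.1.** "Dose modifications will be made only for those AEs thought to be related to everolimus". The section also ties dose changes to the worst toxicity so far. Table 3-2 stops everolimus for "Any other grade 4". Its pneumonitis row points to Table 3-4, and its grade 3 row exempts metabolic events and points to Section 3.3.2.6. It has no row or exemption for hepatitis B.

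**Hematologic rules, Table 3-3.** Grade 4 neutropenia means discontinue. The febrile-neutropenia row means interrupt, then reintroduce one level lower, with no neutrophil limit.

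**The concern.** A reactivation that the investigator judges life-threatening is recorded as grade 4. If it is thought related to everolimus, one table says stop and another leaves restart open. An investigator who uses the Table 3-6 restart departs from Table 3-2, and no sentence expressly says which table prevails.

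The stake is patient safety. Section 3.3.2.1 lists hepatitis B reactivation among the infections seen on everolimus, some of them severe and occasionally fatal. Table 3-6 would permit renewed exposure to an immunosuppressant once the virus is undetectable, without asking whether the patient has recovered clinically. Section 3.1 notes that most of these patients have a surgical option and accept side effects less readily than patients with metastatic disease. The case for rechallenge is therefore weak in localized disease.

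**Working it through.** No arithmetic is needed beyond a count. The check sets the rules side by side.

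**1. Is grade 4 reactivation inside Table 3-6?** Yes. The heading covers all presentations, and its asterisk leads to the footnote that assigns grade 4.

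**2. Is it inside Table 3-2?** Yes, if thought related to everolimus. Section 3.3.2.8 reports sporadic reactivations with everolimus, so that judgement is realistic.

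**3. What does each table say for a related grade 4 reactivation?**

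| Case | Table 3-6 | Table 3-2 | Result |
|---|---|---|---|
| HBV-DNA cleared within 28 days, on 10 or 5 mg | May restart one level lower | Discontinue | Overlap |
| HBV-DNA cleared within 28 days, on 2.5 mg | Restart at 2.5 mg | Discontinue | Overlap |
| HBV-DNA not cleared within 28 days | Discontinue | Discontinue | Agree |
| AST or ALT above 20 x ULN, or clinical liver failure | Not addressed | Separate rows: discontinue | Stop rows apply in their own right |

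**4. Does any sentence rank the tables?** Not expressly. The worst-toxicity sentence points towards stopping. In the other direction, specific rules in 3.3.2 already differ from Table 3-2 at grade 3. For example, stomatitis restarts at a lower dose in 3.3.2.4, while Table 3-2 allows the previous dose if a grade 3 event resolves within 7 days. Table 3-6 might therefore be meant to govern. But where Table 3-2 gives way to a specific rule in writing, it names that rule, and hepatitis B is not named.

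**5. How do the other event rules in 3.3.2 treat grade 4?**

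| Tabulated rule | Grade 4 action |
|---|---|
| Stomatitis (3.3.2.4) | Stop |
| Metabolic events (3.3.2.6) | Stop |
| Pneumonitis (Table 3-4) | Stop |
| Hepatitis C flare (Table 3-7) | "Discontinue everolimus", at any grade |
| Hepatitis B reactivation (Table 3-6) | Restart open |

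Four of the five tabulated rules stop; hepatitis B alone does not. Outside the tables, Section 3.3.2.1 covers infections without a grade split. It asks the investigator to consider interrupting or stopping, and makes a stop mandatory only for invasive systemic fungal infection.

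**6. Febrile neutropenia.** Table 3-3 defines grade 3 neutropenia as below 1 and at least 0.5 x10^9/L, so grade 4 is below 0.5 by inference. Fever at such a count meets both the stop row and the reintroduce row. The asterisk on the febrile row leads only to the rule for interruptions over 28 days.

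**7. How much remains?** For hepatitis B, the overlap needs all of the following: related to everolimus, judged life-threatening, AST and ALT at or below 20 x ULN, no clinical liver failure, and HBV-DNA undetectable within 28 days. Section 8 caps accrual at 18. Patients with detectable HBV-DNA or HBsAg are ineligible (Section 2.1.2.15, Table 3-5).

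**The case against.** The strongest reply is that the text does not force a conflict and leans towards safety. Several parts of it stand.

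- Above the lowest dose, Table 3-6 says everolimus can be restarted. A reader might infer that the protocol requires a restart after a life-threatening reactivation. It does not. The 2.5 mg sentence is best read as fixing the dose when no lower level exists, and an investigator who stops complies with both tables. Section 3.6.1 also allows removal at the investigator's discretion.
- The worst-toxicity sentence applies to hepatitis B as much as to febrile neutropenia, and favours stopping in both.
- A reader might infer that hepatitis B is the only event in 3.3.2 without a mandatory grade 4 stop. Section 3.3.2.1 contradicts that: it names hepatitis B reactivation and leaves most infections to judgement. Hepatitis B is the exception only among the tabulated rules.
- A reader might infer that restart rests on viral load alone. Undetectable HBV-DNA is the only recovery criterion, but Table 3-6 also requires antiviral treatment and a lower dose where one exists. Related clinical toxicities recorded separately keep their own Table 3-2 rows: a generic grade 3 event must recover to grade 1 or baseline, and another grade 4 event stops treatment.
- A single precedence sentence would settle the overlap, and removing rechallenge is partly a clinical preference.

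What survives is narrower. A stated dosing rule lets an investigator restart after a reactivation recorded as grade 4, against the general grade 4 stop rule, and nothing expressly ranks the two. A sentence giving Table 3-6 precedence would remove the inconsistency but keep a restart without a requirement for clinical recovery.

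**Conclusion.** The overlap is real and minor. Table 3-6 permits, under antiviral cover, a restart after a grade 4 hepatitis B reactivation that Table 3-2 would stop. The worst-toxicity sentence favours stopping without settling the matter. The febrile-neutropenia overlap in Table 3-3 is a lesser instance: both rows sit in one table, and the reintroduce row can be read as a tighter form of the grade 3 row.

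The documents give no frequency. That the event is rare is an inference from the accrual ceiling, the hepatitis B exclusions and the separate stop rows. The conclusion also assumes that the event is thought related to everolimus, since otherwise the dose-modification rules do not apply. Some readers might extend the point to the trial's efficacy conclusions, but nothing in the Section 8 design depends on these rows. It is worth correcting because the consequence could be grave and the change is small.

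**What to change.** Amend three tables together:

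1. **Table 3-6:** limit both restart instructions to reactivations recorded as grade 3. Add a line for those recorded as grade 4: stop everolimus and keep the antiviral going for at least 4 weeks after the last dose.
2. **Table 3-2:** add a hepatitis B reactivation row that refers to Table 3-6, as already done for pneumonitis and Table 3-4.
3. **Table 3-3:** limit the febrile-neutropenia row to neutrophils of at least 0.5 x10^9/L, leaving lower counts to the grade 4 row.

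The cost is a few words in one amendment, with no added visits or procedures. The clinical downside is that a rare patient who clears the virus within 28 days loses the rechallenge option. That loss matters more in locally advanced or metastatic disease, which Section 3.4 treats until progression, than in localized disease, where treatment lasts one year.

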3.4 STUDY CALENDAR

1 cycle = 28 days

Evaluations below may be performed within \pm 3 days of indicated time in order to accommodate patient schedules, holidays and weather emergencies. Imaging studies and optional tumor biopsies may be performed within \pm 7 days of indicated time.

Baseline and Restaging evaluation will be performed at the NIH CC. However, mandated laboratory studies and other evaluations may be performed at local laboratory or by local health care providers.

Restaging will be performed approximately every 12 weeks. Treatment can continue for 52 weeks in the absence of unacceptable toxicity or disease progression.

Patients with BHD associated tumors localized to the kidneys will be treated for one year in the absence of unacceptable toxicity or disease progression. Patients with locally advanced or metastatic disease will be treated until disease progression in the absence of unacceptable toxicity.

Abbreviated Title: Phase II everolimus for BHD

Version Date: March 7, 2017

	Screening / Baseline	Day 1	Cycle 1 Day 14	Cycle 2 Day 1	Cycle 2 Day 14	Cycle 3 Day 1	Cycle 3 Day 14	Cycle 4 Day 1	Start of Every Cycle	EOT	Follow up ¹¹	Survival ¹²
Visit no.	1	2	3	4	5	6	7	8	9, 10 etc...		EOT + 28 days	
Treatment days	-14 to -1											
Demography/informed consent	X											
Relevant medical history/current medical conditions	X											
Diagnosis and extent of cancer	X											
Vital signs	X	X*		X		X		X	X	X		
Height	X											
Weight	X	X*		X		X		X	X	X	X	
Physical examination	X ⁸											
ECOG/Karnofsky performance status	X	X*										
EKG ¹	X											
Thyroid function tests	X		Every 12 weeks									
CBC with differential	X		X	X		X		X	X	X	X	
Serum Chemistries ²	X		X	X		X		X	X	X	X	
Fasting serum Lipid Profile ³	X			X		X		X	X	X		
Urinalysis ⁴	X			X		X		X	X			
Serum β hCG (in female patients of childbearing potential)	X			X		X		X	X			
HbA1c, pulse oximetry	X											
PT/PTT	X											

Abbreviated Title: Phase II everolimus for BHD

Version Date: March 7, 2017

	Screening / Baseline	Day 1	Cycle 1 Day 14	Cycle 2 Day 1	Cycle 2 Day 14	Cycle 3 Day 1	Cycle 3 Day 14	Cycle 4 Day 1	Start of Every Cycle	EOT	Follow up ¹¹	Survival ¹²
Visit no.	1	2	3	4	5	6	7	8	9, 10 etc...		EOT + 28 days	
Treatment days	-14 to -1											
Prior/concomitant medications	X											
Adverse events												
Tumor evaluation												
PFT	X											
CT chest/abdomen/pelvis and/or, CT chest plus MRI abdomen/pelvis ⁵	X									X		
CT Neck in patients with known or suspected metastatic disease in the neck ⁶												
CT or MRI for Brain	X											
Bone scans in patients with known or suspected bone metastases ⁷	X ⁸											
FDG-PET in patients with known or suspected metastatic disease	X ⁸											
Optional biopsy (At baseline, archival tumor samples may be used)	X						X					
Everolimus Dosing		Daily										
Follow up survival contact												X
HBV-DNA, HBsAg, HBs Ab, HBc Ab, HCV-RNA-PCR, ANTI- HCV ⁹	X											
HBV DNA ¹⁰									Every 3 - 4 weeks		X	X

Confidential Information

Abbreviated Title: Phase II everolimus for BHD

Version Date: March 7, 2017

	Screening / Baseline	Day 1	Cycle 1 Day 14	Cycle 2 Day 1	Cycle 2 Day 14	Cycle 3 Day 1	Cycle 3 Day 14	Cycle 4 Day 1	Start of Every Cycle	EOT	Follow up ¹¹	Survival ¹²												
Visit no.	1	2	3	4	5	6	7	8	9, 10 etc...		EOT + 28 days													
Treatment days	-14 to -1																							
HCV RNA-PCR ¹⁰				Every 4 – 8 weeks						X	X													
Photographic evaluation of skin lesions ¹³	X	Every 12 weeks																						
All attempts should be made to complete the visits within 72 hours of the day indicated on the evaluation schedule. Visit 2 must be conducted no more than 21 days after the screening visit and 28 days for patient positive for HepB and C.																								
*If clinically indicated.																								
1. Screening ECG is a standard 12 lead and must be performed within 14 days of first dose for patients enrolled and may be repeated at the investigator's discretion if clinically indicated																								
2. Serum Chemistry must include: Albumin, Alkaline phosphatase, ALT (alanine transaminase), AST (aspartate aminotransferase), BUN (blood urea nitrogen), Calcium, Serum chloride, CO2 (carbon dioxide), Creatinine, Direct bilirubin, Gamma-GT (gamma-glutamyl transpeptidase), Glucose test, LDH (lactate dehydrogenase), Phosphorus, Potassium test, Serum sodium, Total bilirubin, Total cholesterol, Total protein, Uric acid.																								
3. Serum fasting lipid profile must include: total cholesterol and triglycerides. Patients should be in fasting state.																								
4. Standard urinalysis dipstick assessment must include: protein, glucose, blood, ketones, and leukocytes.																								
5. Chest, abdomen, pelvis scans need to be repeated at each tumor assessment visit (including if negative at baseline). Scans for complete and partial responses must be repeated at least at 4 weeks but no later than the next scheduled tumor assessment following the first documented response. Skin lesions should be photographed in addition to measuring.																								
6. CT Neck in patients with known or suspected metastatic disease in the neck will be repeated at restaging if positive for metastasis.																								
7. A bone scan or skeletal survey is to be performed at baseline and will be repeated at restaging if positive for metastasis.																								
8. Repeat at restaging only if indicated																								
9. All patients should be screened for hepatitis risk factors and any past illnesses of hepatitis B and hepatitis C as outlined in Sections 2.2. Patients with viral hepatitis B or C risk factors should be screened for Hep B and HCV RNA-PCR.																								
10. Patients on antiviral prophylaxis treatment or positive HBV antibodies should be tested for HBV-DNA every 3 – 4 weeks. Patients with positive HCV-RNA PCR or a history of past infection, even if treated and considered 'cured' – should be followed by HCV-RNA PCR every 4 – 8 weeks.																								
11. Follow up visits conducted at the EOT+28 days visit.																								
12. After progression, an attempt will be made to follow patients to obtain information about survival every three to six months.																								
Legend: wks stands for weeks, EOT for End of Treatment visit																								
13. Photographic evaluation of skin lesions - only in patients with BHD- associated cutaneous manifestations.																								

